Appendix VIII

Specimen Shipment Requisition Form

ECOG-ACRIN – PROTOCOL EA6134

It is required that samples submitted from patients participating in EA6134 be entered and tracked via the online ECOG-ACRIN Sample Tracking System. This form is used only in the event that the STS is inaccessible and then the shipments are to be logged in retroactively, indicating the actual dates of collection and shipment.

Immunologic Monitoring and Cellular Products Laboratory	UPCI Research Pavilion at the Hillman Cancer Center Room L 1.31 [name] [name] [contact] [contact]
------------------------------------------------------------	-----------------------------------------------------------------------------------------------------------------------------------------------------------------------

Ship samples by FedEx Priority Overnight to arrive the next morning unless otherwise directed by the protocol. Do NOT ship on Friday or Saturday, or the day before a legal holiday.

Call the IMCPL ECOG-ACRIN Study Coordinator at [contact] with questions on collection and shipping.

Please complete the following information and include this form in the shipment.

ECOG-ACRIN Patient Sequence Number: _____
 
ECOG-ACRIN Patient Initials: _____
 
Last First
 
Clinical Site: _____
 
Site Contact: _____
 
Telephone Number: _____
 
Fax Number: _____
 
Federal Express® Air Bill No.: _____
 
Date of Shipment: _____

Specimen
Collection Date ____/____/____
MM/DD/YY

Specimen
Collection Time: ____:____:____
(24 hour clock)

Rev. Add13

DREAMseq (Doublet, Randomized Evaluation in Advanced Melanoma Sequencing) a Phase III Trial

Appendix IX

New York Heart Association (NYHA) Classification System

Class	Patient Symptoms
Class I (Mild)	No limitation of physical activity. Ordinary physical activity does not cause undue fatigue, palpitation, or dyspnea (shortness of breath).
Class II (Mild)	Slight limitation of physical activity. Comfortable at rest, but ordinary physical activity results in fatigue, palpitation, or dyspnea.
Class III (Moderate)	Marked limitation of physical activity. Comfortable at rest, but less than ordinary activity causes fatigue, palpitation, or dyspnea.
Class IV (Severe)	Unable to carry out any physical activity without discomfort. Symptoms of cardiac insufficiency at rest. If any physical activity is undertaken, discomfort is increased.

Rev. Add13 **DREAMseq (Doublet, Randomized Evaluation in Advanced Melanoma Sequencing) a
Phase III Trial**

Rev. 12/15, 6/16

[figure not shown]
Appendix X

MANAGEMENT ALGORITHMS FOR ENDOCRINOPATHY, GASTROINTESTINAL, HEPATIC, NEUROLOGICAL, PULMONARY, RENAL, AND SKIN ADVERSE EVENTS

NOTE: In the event that the dosing management outlined in Section [5.4.2](#) conflicts with [Appendix X](#) Management Algorithms, the EA6134 recommendation is to follow the Section [5.4.2](#) management guidelines.

Endocrinopathy Management Algorithm

[figure not shown]
Rule out non-inflammatory causes. If non-inflammatory cause, treat accordingly and continue immuno-oncology (I-O) therapy.
Consider visual field testing, endocrinology consultation, and imaging.

Patients on IV steroids may be switched to an equivalent dose of oral corticosteroids (e.g. prednisone) at start of tapering or earlier, once sustained clinical improvement is observed. Lower bioavailability of oral corticosteroids should be taken into account when switching to the equivalent dose of oral corticosteroids.

GI Adverse Event Management Algorithm

[figure not shown]
Rule out non-inflammatory causes. If non-inflammatory cause is identified, treat accordingly and continue I-O therapy. Opiates/narcotics may mask symptoms of perforation. Infliximab should not be used in cases of perforation or sepsis.

Patients on IV steroids may be switched to an equivalent dose of oral corticosteroids (e.g. prednisone) at start of tapering or earlier, once sustained clinical improvement is observed. Lower bioavailability of oral corticosteroids should be taken into account when switching to the equivalent dose of oral corticosteroids.

Hepatic Adverse Event Management Algorithm

Rule out non-inflammatory causes. If non-inflammatory cause, treat accordingly and continue I-O therapy. Consider imaging for obstruction.

[figure not shown]
Patients on IV steroids may be switched to an equivalent dose of oral corticosteroids (e.g. prednisone) at start of tapering or earlier, once sustained clinical improvement is observed. Lower bioavailability of oral corticosteroids should be taken into account when switching to the equivalent dose of oral corticosteroids.

*I-O therapy may be delayed rather than discontinued if AST/ALT ≤ 8 x ULN and T.bili ≤ 5 x ULN.

**The recommended starting dose for grade 4 hepatitis is 2 mg/kg/day methylprednisolone IV.

Neurological Adverse Event Management Algorithm

[figure not shown]
Rule out non-inflammatory causes. If non-inflammatory cause, treat accordingly and continue I-O therapy.

Patients on IV steroids may be switched to an equivalent dose of oral corticosteroids (e.g. prednisone) at start of tapering or earlier, once sustained clinical improvement is observed. Lower bioavailability of oral corticosteroids should be taken into account when switching to the equivalent dose of oral corticosteroids.

Pulmonary Adverse Event Management Algorithm

[figure not shown]
Rule out non-inflammatory causes. If non-inflammatory cause, treat accordingly and continue I-O therapy. Evaluate with imaging and pulmonary consultation.

Patients on IV steroids may be switched to an equivalent dose of oral corticosteroids (e.g. prednisone) at start of tapering or earlier, once sustained clinical improvement is observed. Lower bioavailability of oral corticosteroids should be taken into account when switching to the equivalent dose of oral corticosteroids.

Renal Adverse Event Management Algorithm

[figure not shown]
Rule out non-inflammatory causes. If non-inflammatory cause, treat accordingly and continue I-O therapy

Patients on IV steroids may be switched to an equivalent dose of oral corticosteroids (e.g. prednisone) at start of tapering or earlier, once sustained clinical improvement is observed. Lower bioavailability of oral corticosteroids should be taken into account when switching to the equivalent dose of oral corticosteroids.

Skin Adverse Event Management Algorithm

Rule out non-inflammatory causes. If non-inflammatory cause, treat accordingly and continue I-O therapy.

Patients on IV steroids may be switched to an equivalent dose of oral corticosteroids (e.g. prednisone) at start of tapering or earlier, once sustained clinical improvement is observed. Lower bioavailability of oral corticosteroids should be taken into account when switching to the equivalent dose of oral corticosteroids.

*Refer to NCI CTCAE v4 for term-specific grading criteria.

Rev. Add13 **DREAMseq (Doublet, Randomized Evaluation in Advanced Melanoma Sequencing) a Phase III Trial**

Rev. 11/16

Appendix XI

Strong inducers of CYP3A4 or CYP2C8

Any medications or substances that are strong inhibitors or inducers of CYP3A4 or CYP2C8 are ineligible. Current use of, or intended ongoing treatment with: herbal remedies (e.g., St. John's wort), or strong inhibitors or inducers of P-glycoprotein (Pgp) or breast cancer resistance protein 1 (Bcrp1) should also be excluded.

Below are a few examples of the agents that are prohibited while on study treatment:

PROHIBITED – strong inducers of CYP3A4 or CYP2C8, since concentrations of dabrafenib may be decreased	
Class/Therapeutic Area	Drugs/Agents
Antibiotics	Rifamycin class agents (e.g., rifampin, rifabutin, rifapentine),
Anticonvulsant	Carbamazepine, oxcarbazepine phenobarbital, phenytoin, s-mephenytoin
Miscellaneous	bosentan, St. John's wort
PROHIBITED – Strong inhibitors of CYP3A4, or CYP2C8 since concentrations of dabrafenib may be increased	
Class/Therapeutic Area	Drugs/Agents
Antibiotics	Clarithromycin, telithromycin, troleandomycin
Antidepressant	Nefazodone
Antifungals	Itraconazole, ketoconazole, posaconazole, voriconazole
Hyperlipidemia	Gemfibrozil
Antiretroviral	ritonavir, saquinavir, atazanavir
Miscellaneous	Conivaptan

Because the lists of these agents are constantly changing, it is important to regularly consult a frequently-updated list; medical reference texts such as the Physicians' Desk Reference may also provide this information. As part of the enrollment/informed consent procedures, the patient will be counseled on the risk of interactions with other agents, and what to do if new medications need to be prescribed or if the patient is considering a new over-the-counter medicine or herbal product.

Rev. Add13 **DREAMseq (Doublet, Randomized Evaluation in Advanced Melanoma Sequencing) a
Phase III Trial**

Rev. 11/16

Appendix XII

What to do if a patient comes in with possible immunotherapy-induced Myocarditis?

[name] and [name] (Vanderbilt)

Detection:

Troponin – screening per Section [7](#)

If troponin elevated, then obtain diagnostic workup, including:

Clinical examination for signs of heart failure, ischemia, arrhythmia and skeletal muscle myositis.

EKG, to rule out myocardial ischemia

For myocarditis, special attention to heart block, PR prolongation, QRS duration

CK (for concomitant myositis), CK-MB

Assess cardiac function via cardiac imaging

Echo (structural heart disease)

Consider cardiac MRI if available

Monitoring

If troponin elevated but not symptomatic and no arrhythmia, then hold immunotherapy and obtain troponin every 2-3 days with concurrent CK, CK-MB, and EKG until normalized. If normalized within 2 weeks, may proceed with treatment otherwise hold further therapy.

If troponin elevated and patient symptomatic and/or suspected myocarditis, admit to the hospital:

Monitor troponin, CK, CK-MB

Continuous cardiac monitoring

EKG at least daily

Cardiology consult

If other cardiac causes for patient's symptoms are ruled out, and the most likely diagnosis is myocarditis, a myocardial biopsy is strongly encouraged to confirm immune mediated myocarditis. Cardiac MRI may be an alternative to myocardial biopsy for diagnosis.

Treatment of presumed or confirmed myocarditis

Early cardiology consultation is strongly encouraged. Since most cardiologists are unaware of immune related adverse events, cardiology education about the therapies and adverse effects is important. Particularly, since EKG manifestations (specifically, heart block) appear to be an early manifestation of this entity, would favor consideration for pacemaker placement.

The optimal approach for treatment of myocarditis has not been established. Since this toxicity has caused patient deaths aggressive management is encouraged. Corticosteroids (see below) may be started while pending definitive diagnosis, if myocarditis is suspected.

Methylprednisolone 2mg/kg IV daily

Alternatively, methylprednisolone 1g daily (dose used for acute allograft rejection in cardiac transplantation) could be considered.

Based on the experience with other immune-related adverse events and cellular-mediated cardiac transplantation, other agents to consider include:

Infliximab

Anti-thymocyte globulin (ATG)

Mycophenolate mofetil

Tacrolimus

Investigational Studies

Defining mechanisms of toxicity is the best means to develop preventative and treatment strategies for immune mediated myocarditis.

If myocardial biopsy is obtained, then should get the following:

Formalin-fixed tissue (routinely done)

Frozen tissue (or snap frozen tissue)

In case of patient death, an autopsy can be helpful to help future cases

Education in terms of getting autopsy

Make sure whole set of organs is autopsied: skeletal muscle, endocrine (pituitary), liver, kidney

Rev. Add13

DREAMseq (Doublet, Randomized Evaluation in Advanced Melanoma Sequencing) a Phase III Trial

Rev. 5/17,
10/17

Rev. Add10

Appendix XIII

Ancillary for Tobacco Use Assessment: EAQ16T

Study Co-Chairs: [name], [name], [name], [name], [name]

Patients registered to the selected ECOG-ACRIN trials are eligible to participate in this ancillary study, once the appropriate amendment incorporating the study is activated.

The Ancillary for Tobacco Use Assessment is a project that seeks to address questions about patient-reported tobacco use and smoking behaviors that may span several studies and/or diseases. The tobacco use ancillary is embedded into parent protocols, with participation in the ancillary informed in the parent consent form and participation determined via providing email address to the sites. The general objectives of the tobacco use ancillary are not specific to any single parent protocol; however, specific objectives may be included in the parent or related parent protocols.

A significant proportion of cancer patients are current smokers at the time of cancer diagnosis,¹⁻⁵ and there are known risks associated with continued smoking following cancer diagnosis. These include decreased survival time; increased complications from surgery, radiation, and chemotherapy; and increased risk of second primary tumors.⁶⁻¹¹ As such, the National Comprehensive Cancer Network (NCCN), the American Association of Cancer Research (AACR) and the American Society of Clinical Oncology (ASCO) have identified persistent smoking as a modifiable risk factor and recommend cessation counseling for cancer patients who smoke. Although evidence-based guidelines for treating tobacco dependence exist,¹² they have not yet been well-integrated into cancer care settings. Moreover, knowledge regarding the scope and patterns of tobacco use among cancer patients is limited. As a critical step in closing this knowledge gap, the NCI-AACR Cancer Patient Tobacco Use Assessment Task Force developed the Cancer Patient Tobacco Use^{1-4,13,14} Questionnaire (C-TUQ). Through this ancillary, the modified C-TUQ measures will be administered to participants enrolling in selected Phase II and Phase III ECOG ACRIN (EA) therapeutic trials.

The major questions may be summarized:

1. What is the smoking status of cancer patients enrolled on EA clinical trials?
2. Do patients quit smoking or try to quit smoking after receiving a cancer diagnosis?
3. What forms of tobacco use do patients engage in?
4. What assistance do patients use or receive to try to quit?
5. How does tobacco use, other forms of tobacco use, and/or environmental tobacco exposure affect patient's treatment toxicity, patient-reported physical and psychological symptoms, trial adherence, and therapeutic outcomes?

When patients consent to participate, they will be asked to provide a contact email address and that address along with their registration information will be sent directly from the parent trial's registration system to ECOG-ACRIN Systems for Easy Entry of Patient Reported Outcomes (EASEE-PRO), and the patient will be automatically registered into EASEE-PRO for participation. To activate their account for self-directed web entry of surveys, the system will send an activation message to the contact email address that will explain how to activate their

account for self-directed web entry of surveys. After their account is activated, the patient will be able to complete questionnaires using a secure browser interface from any web enabled computer, tablet, or mobile device.

Measures

The selected Core and Extension C-TUQ items will be assessed. The 4-item Short Form PROMIS® for anxiety and depression, the Lung Cancer Stigma Scale, and six symptom items (general pain, fatigue, nausea, cough, insomnia, shortness of breath) from FACIT (Functional Assessment of Chronic Illness Therapy) together with modifications of these same six questions to address the degree of bother associated with each symptom will be administered as well. Additionally, we will ask participants' perceptions of how smoking improves or worsens each of the six symptom experience. All these items will be compiled into Survey of Tobacco Use (STU) (baseline and follow-up).

Contents and Corresponding Questions in Survey of Tobacco Use (STU)

Dimension	Source of Measures	Baseline STU	Follow-up STU
Basic Tobacco Use Information	C-TUQ	Q1 – Q5	Q1-Q2
Tobacco Use in Relation to Cancer Diagnosis and Treatment	C-TUQ	Q6 – Q7	Q3
Smoking Cessation, Cessation Products, and Assistance Methods	C-TUQ	Q8 – Q13	Q4 – Q9
Use of Other Products	C-TUQ	Q14	Q10
Second-Hand Smoke Exposure	C-TUQ	Q15-Q16	Q11-Q12
Psychological Symptoms	PROMIS Lung Cancer Stigma Scale	Q17-Q18	Q13-Q14
Physical Symptoms	FACIT	Q19	Q15
Sociodemographics		Q20-21	

NOTE: In order to minimize ambiguity and assure that patients are oriented to answer appropriately, the specific phrasing of items may vary depending specific cancer type and treatment.

Tobacco Use. The selected Core and Extension C-TUQ items (from categories of Basic Tobacco Use Information, Tobacco Use in Relation to Cancer Diagnosis and Treatment, Smoking Cessation/Cessation Products/Assistance Methods, Use of Other Products, and Second-Hand Smoke Exposure) will be assessed in the baseline and follow-up Survey of Tobacco Use.

Oncology Provider Assistance. C-TUQ Question 13 assesses “cancer doctors” Advise. We will add 4 As to assess participants' reported 5As (Ask (Q12a), Advise (Q12b), Assess (Q12c), Assist (Q12d-Q12f), and Arrange follow-up (Q12g), as in Baseline STU).⁸⁰

Psychological Symptom Assessment. Anxiety & Depression: (*The Patient Reported Outcomes Measurement Information System (PROMIS®)*). We will administer the 4-item Short Form PROMIS® for anxiety and depression (Q17 in Baseline STU). Stigma: The Lung Cancer Stigma scale measures the extent to which shame is internalized (Q18 in Baseline STU).⁸¹

Physical Symptom Assessment *Physical Symptom Assessment (Functional Assessment of Chronic Illness Therapy (FACIT)). FACIT, a measurement system with a collection of quality-of-*

life questionnaires, expands the more familiar FACT (Functional Assessment of Cancer Therapy) questionnaires into other chronic illness and conditions. FACIT consists of many individual questions to assess various symptoms from the patient perspective. We will use 6 FACIT items, selected based on the therapeutic regimens, expected toxicity, and malignancy type of the parent trials. In addition, we have created modifications of these same six questions to address the degree of bother associated with each symptom. The symptoms of general pain, fatigue, nausea, cough, sleep difficulty, and shortness of breath will be assessed, first using the standard and validated FACT item, and then asking the degree of “bother” imposed by each symptom, on the same 5-point scale. These clusters of symptoms were specifically chosen based on potential interactions between tobacco use and longitudinal symptoms.

Sociodemographic Variables. Sociodemographic variables, including age, sex, zip code, and race/ethnicity are collected for all NCTN trial participants at registration. At baseline, participants will provide information on marital status (Q20 in Baseline STU) and education level (Q21 in Baseline STU) as part of the tobacco supplemental assessment.

Cancer Treatment Variables. Clinical variables including date of diagnosis, malignancy type (smoking related vs. non-smoking related, cancer stage), and treatment details (i.e. types and dates of surgery, chemotherapy, and/or radiation received), along with disease status and survival, will be captured in Medidata Rave via the parent protocol and will be available for analysis of the ancillary. Provider-assessed adverse events will also be captured via the parent protocol in Medidata Rave, using case report forms commonly used across the NCTN and using standard data elements.

Assessments

All items in Survey of Tobacco Use will be administered using the EASEE-PRO system. The advantage of our virtual electronic data capture system is that our proposed assessments will not be limited to, or dependent upon, patient trial visits. Confidential and potentially stigmatizing information can be provided without requiring direct contact with the care team.

Timing of Assessments

Given the critical questions that remain¹³ about the timing of conducting tobacco use assessments, we have carefully chosen to collect tobacco assessment data at trial enrollment, 3 and 6 month follow-up. For tobacco treatment trials, 6 month follow-up is the recommended primary outcome time point. By 6 month follow-up, most cancer treatment-related quitting activity⁶², cancer treatment initiation of therapy, and FDA-approved smoking cessation medication regimens will be completed. Adverse events during treatment will have been observed.

Statistical Considerations and Analysis Plans

The analysis plans described below are planned for a combined analysis of the data from the selected ECOG-ACRIN trials. Consistency in the effects over the studies would be examined in this analysis.

1. **CHANGES IN SMOKING STATUS AND EXPOSURE.** At baseline, combustible tobacco use (1a) will be characterized by smoking status (never smoker, former smoker, and current smoker based on Baseline STU Qs 1 and 5), other forms of tobacco use (1b) will be a composite variable determined by non-cigarette items (based on Baseline STU Q7 and Q14), and environmental tobacco smoke (ETS) level (1c) will be determined by current household and work exposure (Baseline STU Qs 15-16). At follow-up, combustible tobacco use (1a) will be examined by smoking status (Follow-up STU Qs 1 and 2), other forms of tobacco use (1b) will be determined by Follow-up STU Q10, and ETS level (1c) will be

determined by 30 day household and work exposure (Follow-up STU Qs 11-12). We will examine tobacco use at baseline, 3 and 6 month follow-up, and change in status (abstinence in combustible tobacco, abstinence of other forms of tobacco use, and change in exposure to smoke-free home and work) using summary statistics (frequency and proportion). We will explore the effects of sociodemographic and cancer treatment factors on smoking status using logistic regression (comparing smokers and non-smokers). We will also evaluate factors associated with changes in smoking status.

2. **TREATMENT TOXICITY.** The selected trials capture information about adverse events during treatment using NCI's Common Terminology Criteria for Adverse Events, Version 4. Toxicities are measured at each treatment visit and graded according to severity, with grade 1 corresponding to mild toxicity and grade 5 signifying a lethal adverse event. We will determine each patient's worst degree toxicity across all event types and treatment visits and will compare the distribution of worst degree grades between smokers and non-smokers and between patients with environmental tobacco exposure and those without exposure using exact tests. We will also examine the distribution of worst degree grades between users with different form of tobacco use. In addition, we will explore the effects of tobacco use on dose modifications (yes vs. no) using logistic regression, with each patient's dose modification status determined across all treatment visits.
3. **SYMPTOM BURDEN.** Tobacco variables will be conceptualized as described in the section of **CHANGES IN SMOKING STATUS AND EXPOSURE**. Tobacco use status (as measured at baseline, 3 and 6 month follow-up) will be compared to physical and psychological symptom burden (as measured at each corresponding time points). At 3 and 6 month follow-up, we will also examine the association between tobacco use changes and changes in symptom burden. We will explore the effects of sociodemographic and cancer treatment factors on symptom burden using repeated measures mixed effects models. As an example of statistical power, we consider the PROMIS SF-4 depression measure. We assume that 1500 patients will be enrolled across the 8 parent studies over 13 months, and that 20% are smokers. We assume that 85% of patients will have assessments at 6 months. Given groups of these sizes (26 quitters and 230 still-smokers) and standard deviation of 4.08 for the PROMIS SF-4 depression scale, there will be 83% power to detect a difference in change scores of 2.5 between groups using a two-sample t-test with Type I error of 5%. The minimally important difference for this instrument is 2.2.⁷⁹
4. **CESSATION PATTERNS AND TREATMENT.** At baseline we will explore pre-treatment combustible tobacco use patterns (STU Q6a and Q6b), quitting behaviors (STU Q13), behavioral program utilization (STU Q11) and oncology provider support (5As, STU Q12), and smoking cessation medication use (STU Q10). At follow-up we will explore post-treatment combustible tobacco use patterns (STU Q3a-Q3e), quitting behaviors (STU Q9), behavioral program utilization (STU, Q7) and oncology provider support (5As, STU Q8), and smoking cessation medication use (STU Q6). We will explore the effects of sociodemographic and cancer treatment factors on these variables. We will examine associations of quitting behaviors and behavioral and medication utilization with tobacco use status (as outlined in the section of **CHANGES IN SMOKING STATUS AND EXPOSURE**) at baseline and on respective 3 and 6 month tobacco outcomes. These analyses will be descriptive in nature. Summary statistics (frequency, proportions, and 95% confidence intervals) will be used.
5. **TRIAL OUTCOMES.** We will compare treatment duration between smokers and non-smokers and between patients with environmental tobacco exposure and those without exposure. Cumulative incidence/competing risk methods will be used to estimate time to treatment discontinuation for adverse events, disease progression, completion per protocol,

or other causes. Gray's test will be used to test for differences in the cumulative incidence distributions.⁷⁸ Differences in the distribution of reasons for discontinuation of treatment will be examined using exact tests. Relative dose intensity is defined as the ratio of actually delivered dose intensity to the planned dose intensity. The effects of tobacco use and exposure on relative dose intensity ($\geq 90\%$ vs. $< 90\%$) will be explored using logistic regression. Differences in the primary endpoint and important secondary endpoints will be examined using log rank test and exact test (as appropriate).

Data collected in the tobacco use project will support a range of analyses. Precise estimates of power will depend on the prevalence of smoking at baseline among study participants, the proportion whose smoking status changes, and the duration and adequacy of follow-up.

References

2. Gritz E. Rationale for Treating Tobacco Dependence in the Cancer Setting. Conference presentation at: Treating Tobacco Dependence at the National Cancer Institute's Cancer Centers. December 2009.

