The NCI-AACR Cancer Patient Tobacco Use Assessment Task Force developed the Cancer Patient Tobacco Use^{1–4,13,14} Questionnaire (C-TUQ). We propose that administering selected C-TUQ items to participants enrolling in 8 Phase II and Phase III ECOG ACRIN (EA) therapeutic trials will add value to parent trial research questions by advancing the field. Specifically, among patients with varied cancers (tobacco-related and non tobacco-related) and cancer treatments, we will administer C-TUQ questions at EA trial enrollment and 3 and 6 month follow-up.

We have the following aims:

1. **Treatment toxicity:** To determine the effects of tobacco, operationalized as combustible tobacco (1a), other forms of tobacco (1b), and environmental tobacco exposure (ETS) (1c) on provider-reported cancer-treatment toxicity (adverse events (both clinical and hematologic) and dose modifications).
2. **Symptom burden:** To determine the effects of tobacco on patient-reported physical symptoms and psychological symptoms.
3. **Cessation patterns and treatment:** To examine quitting behaviors and behavioral counseling/support and cessation medication utilization.
4. **Trial outcomes:** To explore the effect of tobacco use and exposure on treatment duration and relative dose intensity, and on therapeutic benefit, of 8 selected EA trials.

The findings will advance the nascent field of tobacco use in the context of cancer care by: 1) longitudinal assessment of cigarette smoking, other forms of tobacco use and secondhand smoke exposure at trial enrollment and at 3 and 6 month follow-up; 2) increase knowledge about the effects of tobacco use and exposure on treatment toxicity, physical and psychological symptoms and 3) oncology provider delivery, and 4) patient's perceptions of stigma and utilization of behavioral and pharmacological treatment of tobacco dependence. Finally, the use of this assessment would provide a unique additional value to the hypothesis

of this trial, by allowing investigation of previously unanswered questions about the effects of tobacco use and exposure on trial adherence and outcomes among patients with smoking-related and non-smoking related cancers.

2. Objectives

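### The pooled tobacco analyses of toxicity and trial outcomes (Appendix XIII, items 2 and 5) do not state stratification or adjustment by parent trial, so differences between trials can confound them

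*Combined protocol and SAP*

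**What the plan says.** Section 1.10 places the tobacco assessment in patients "enrolling in 8 Phase II and Phase III ECOG ACRIN (EA) therapeutic trials", and describes the population as "among patients with varied cancers (tobacco-related and non tobacco-related) and cancer treatments".

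Appendix XIII, Statistical Considerations and Analysis Plans, opens: "The analysis plans described below are planned for a combined analysis of the data from the selected ECOG-ACRIN trials". The next sentence is the only reference to parent trial as a factor in the analysis: "Consistency in the effects over the studies would be examined in this analysis". No method is given for it.

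Item 2 (treatment toxicity) takes each patient's worst grade over all event types and visits and "will compare the distribution of worst degree grades between smokers and non-smokers". It does the same for environmental exposure, in both cases with exact tests. Dose modification is analysed by logistic regression with no covariates listed.

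Item 5 (trial outcomes) uses Gray's test for time to treatment discontinuation, exact tests for reasons for discontinuation, and logistic regression for relative dose intensity. It adds: "Differences in the primary endpoint and important secondary endpoints will be examined using log rank test and exact test", qualified as applying where appropriate.

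Item 3 supplies the sample size: "We assume that 1500 patients will be enrolled across the 8 parent studies over 13 months, and that 20% are smokers".

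**The concern.** Parent trial can be related to both sides of the comparison. Smoking prevalence is likely to differ between trials of tobacco-related and other cancers. Toxicity, time on treatment and survival depend on disease and regimen. Because smoking is observed and not assigned, a pooled comparison of smokers with non-smokers combines any within-trial tobacco effect with the differences between trials. A spurious tobacco effect could appear, or a real one could be hidden.

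Elsewhere the same document states such control when it is meant. Section 9.4 names a stratified log-rank test and a Mantel-Haenszel test stratified by performance status and LDH. Sections 9.7 and 11.2.4 adjust the multi-source genetic analyses for centre or clinical protocol. Items 2 and 5 of Appendix XIII state neither. What is at stake is the answer to exploratory objectives 2.5.1 (toxicity and dose modification) and 2.5.4 (treatment duration, dose intensity and benefit).

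**Working it through.** **The plan's own figure.** The only power statement in the tobacco plan is in item 3: 83% for 26 quitters against 230 continuing smokers, difference 2.5, SD 4.08, 5% type I error (taken as two-sided).

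- Group total: 1500 × 0.20 × 0.85 = 255, against 26 + 230 = 256.
- Standard error: 4.08 × √(1/26 + 1/230) = 0.844. Standardised difference: 2.5/0.844 = 2.96.
- Power: Φ(2.96 − 1.96) = 84.2%, or 83.9% by the noncentral t.

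The figure reproduces and is not in dispute. No power or error figure is given for items 2 or 5.

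**Inputs for the check.** From the documents: 1500 patients, 8 trials, 20% smokers overall. Assumed: equal trial sizes; outcome reduced to grade 3 or higher (a simplification of worst grade); and trial-level rates.

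- The smoking range of 10-30% is the one Section 1.10 gives for cancer patients generally. Using it as the spread between trials is an assumption.
- The toxicity range of 10-60% is guided by regimens described in this document: 9% for nivolumab (Section 1.4), 32% + 3% = 35% for dabrafenib plus trametinib (Section 1.8, Table 2), and 49% and 59% for the ipilimumab-nivolumab combination (Section 1.5 and Appendix XVI). These are regimen rates in melanoma, not rates of the 8 trials.

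**Bias by hand, no tobacco effect in any trial.** Let trial i have smoking rate s and toxicity rate t. The pooled toxicity rate is Σst/Σs in smokers and Σ(1−s)t/Σ(1−s) in non-smokers. Take s evenly spaced over 10-30% and t over 10-60%, in the same order.

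- The mean of s is 0.20 and of t is 0.35. The covariance is 0.20 × 0.50 × (63/12)/49 = 0.0107.
- Smokers: (0.20 × 0.35 + 0.0107)/0.20 = 0.404.
- Non-smokers: (0.35 − 0.0807)/0.80 = 0.337.
- Crude odds ratio: (0.404/0.596)/(0.337/0.663) ≈ 1.33, although every within-trial odds ratio is 1.
- With 300 smokers and 1200 non-smokers the standard error is √(0.404 × 0.596/300 + 0.337 × 0.663/1200) = 0.031. So z ≈ 0.067/0.031 ≈ 2.1 and the rejection rate is about 57%, in line with the simulation below.

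**Simulated false-positive rate of the pooled Fisher test (nominal 5%).**

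| Smoking across trials | Toxicity across trials | Random pairing | Perfectly aligned |
|---|---|---|---|
| 10-30% | 10-60% | 11% | about 57% |
| 10-30% | 20-50% | 7% | 24% |
| 10-30% | 30-50% | 6% | 13% |
| 15-25% | 10-60% | 7% | 18% |
| 15-25% | 20-50% | 5% | 9% |
| 15-25% | 30-50% | 5% | 7% |

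The Cochran-Mantel-Haenszel test stratified by trial stays at about 5%.

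**A second set of assumptions** splits the trials 4 and 4, aligned, with no true effect. Smoking 15%/25% with toxicity 40%/60% gives a smoker rate of (0.15 × 0.40 + 0.25 × 0.60)/0.40 = 0.525 and a non-smoker rate of (0.85 × 0.40 + 0.75 × 0.60)/1.60 = 0.494. The odds ratio is 1.13; rejection is 16% pooled and 5% stratified. Smoking 10%/30% with toxicity 30%/60% gives an odds ratio of 1.46; rejection is 83% and 6%. If either smoking or toxicity is equal across trials, the odds ratio is 1.00 and both tests reject about 4-6%.

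**Masking.** With a true within-trial odds ratio of 1.5, smoking 10-30% and toxicity 10-60%, pooled power is 69% under random pairing and 7% when the orderings are opposite. Stratified power is about 80%. If trials do not differ, power is 86% pooled and 87% stratified, so stratifying costs nothing material.

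**The case against.** The text is silent on strata. A reader might infer that it prescribes unstratified tests on one undifferentiated sample, but it does not say so, and the logistic models do not exclude a trial term. That stands, and it is why the point is that stratification is not stated.

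A reader might also infer that survival will be pooled across cancers in a single log-rank test. The documents do not settle this. The sentence carries a where-appropriate qualifier, and parent trials need not share a primary endpoint; in EA6134 it is the 2-year survival rate, tested by Mantel-Haenszel.

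The consistency check has value. It needs trial-specific effects, which are free of between-trial confounding, and could expose a spurious pooled result. It does not repair the pooled p-value: with no effect in any trial, the effects are perfectly consistent and the pooled test can still reject. Malignancy type and treatment details are said to be available, but no test in items 2 or 5 uses them.

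The size is assumed. The 57% needs perfect alignment and wide spreads, and inflation may be negligible. The toxicity range mixes treatment-related rates with a plan that counts all event types, and a two-regimen trial such as EA6134 would lie between its regimens' rates.

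The aims are exploratory, and Section 2.5 keeps them out of the clinical study report. Item 3 already considers cancer treatment factors, and no need for change there was shown.

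**Conclusion.** The concern holds for items 2 and 5. The pooled comparisons are open to confounding by parent trial, and no stated feature of those tests removes it. The condition is that both smoking prevalence and toxicity or outcome differ between trials. That is plausible given the chosen mix of cancers and treatments, but the documents give no rates by trial to establish it.

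Under the widest evenly spread assumptions, false positives are about 11% with random pairing and about 57% at worst, against about 5% stratified. The mildest spreads give about 5-13%, and intermediate aligned cases reach 18-24%. These figures concern a binary toxicity outcome; nothing was simulated for Gray's test, the log-rank test or the logistic models, where the argument is by the same mechanism.

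A reader should not infer that the main trial is compromised. Only exploratory objectives 2.5.1 and 2.5.4 are affected. The EA6134 primary result, sample size and monitoring do not depend on this analysis.

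**What to change.** Limit the change to Appendix XIII, items 2 and 5:

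- Stratify by parent trial the exact tests of worst grade (or use an ordinal Cochran-Mantel-Haenszel test) and the exact tests of discontinuation reasons.
- Stratify Gray's test by parent trial.
- Where trials share an endpoint, stratify the log-rank or exact test of that endpoint by parent trial. Where they do not, report by trial.
- Include parent trial in the logistic models for dose modification and relative dose intensity.
- Define the consistency check as a tobacco-by-trial interaction, reported beside the stratified result.

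Parent trial is known for every patient, so no new data or patients are needed. The loss is a negligible amount of information from strata with few smokers. Because the ancillary is embedded in several parent protocols, the shared text must be kept aligned across them.
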